The Kruskal-Wallis test is a non-parametric statistical test used to determine if there's a significant difference between the medians of three or more independent groups. It's an alternative to the one-way ANOVA when the data doesn't meet the assumptions of normality or equal variances.

STATISTICAL ANALYSIS OVERVIEW:

This present study contains six arms whose descriptions have been provided in the brief summary. The statistical analysis was performed using IBM SPSS version 23. The normality was assessed using Shapiro – wilks test and Q -Q plots. Since the groups do not follow the normal distribution Kruskal – Wallis test to test the statistical significance of post operative sensitivity among the groups. Mann – whitney U test was used to assess the post operative sensitivity among the control groups.

GROUPS INVOLVED:

CONTROL GROUPS:

GROUP 1: Total Etch (TE) Control Group

GROUP 2: Self Etch (SE) Control Group

TEST GROUPS:

GROUP 2: TE - GLUMA Application After Acid Etching

GROUP 3: TE - GLUMA Application Prior to Acid Etching

GROUP 5: SE - GLUMA Application Prior to Acid Etching

GROUP 6: SE - GLUMA Application After Acid Etching

NULL HYPOTHESIS:

The null hypothesis states that there is no statistically significant difference in post operative sensitivity on GLUMA application etching before or after total etching or self-etching followed by composite restoration of the carious teeth.

SAMPLE SIZE CALCULATION:

For this clinical trial, a sample size of 504 restorations was calculated to be sufficient for detecting statistical difference using G* power software (α probability error – 0.05 and effect size – 0.2).

TYPE OF ANALYSIS:

The type of trial is a Noninferiority trials. By definition a non – inferiority trial tests whether a new experimental treatment is not unacceptably less efficacious than an active control treatment already in use. With continuous improvements in health technologies, standard care, and clinical outcomes, the incremental benefits of newly developed treatments may be only marginal over existing treatments. (Hahn S. Understanding noninferiority trials. Korean journal of pediatrics. 2012 Nov 23;55(11):403.)

This test is a non - inferiority trial hence the six groups have GLUMA application before etching of a composite restoration which is not unacceptably less efficacious in reducing post operative sensitivity in composite restoration of a carious tooth.

PROCEDURE:

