All statistical analyses were performed using non-parametric tests due to the non-normal distribution of the data, as confirmed by both the **Kolmogorov–Smirnov** and **Shapiro–Wilk** tests

($p < 0.001$). Descriptive statistics including mean and standard deviation (Mean \pm SD) were calculated for each of the six desensitizer groups at different time points: Pre-operative, 24 hours, 48 hours, and 1 week post-operative sensitivity, measured using the Visual Analog Scale (VAS).

For intergroup comparisons across all six desensitizer protocols, the **Kruskal–Wallis test** was used independently for each time point. This non-parametric method was selected to assess statistically significant differences in median VAS ranks among the groups, given the violation of normality assumptions. A separate p -value was generated for each time point:

- Pre-operative VAS: $p = 0.003$ (significant)
- 24-hour VAS: $p = 0.126$ (not significant)
- 48-hour VAS: $p = 0.050$ (borderline)
- 1-week VAS: $p = 0.013$ (significant)

Pairwise comparisons between the **Total-etch control** and **Self-etch control** groups were performed using the **Mann–Whitney U test**. This analysis revealed a statistically significant difference in pre-operative VAS scores ($p = 0.012$), while post-operative scores showed no significant differences at 24 hours ($p = 0.337$).

Mean pain scores (VAS) were also summarized for each group at all four-time intervals. The **self-etch Gluma prior to etching group consistently showed the lowest VAS scores** at all time points, suggesting reduced post-operative sensitivity in this group.

Given the minimal differences in outcome scores among the other groups, and the slightly better performance of the self-etch GLUMA prior to etching group, the data suggest that **most treatment protocols were non-inferior** to the best-performing group. Therefore, the trial was interpreted as

a **non-inferiority study**, evaluating whether the other etching and desensitizing protocols were not clinically worse than the most effective group.

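### The SAP concludes non-inferiority with no margin and a comparator taken from the results, so the conclusion is unsupported, and no Gluma arm is compared directly with its own control.

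*Combined protocol and SAP*

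**What the plan says.** In the combined protocol and SAP, the Type of Analysis section states: "The type of trial is a Noninferiority trials". It gives a general definition that refers to an active control already in use, but no margin and no named control. It also describes all six groups as receiving Gluma, although two arms are no-desensitizer controls.

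The rest of the plan is about difference. The primary research question in the Detailed Description asks whether Gluma reduces sensitivity. The SAP null hypothesis is that "there is no statistically significant difference in post operative sensitivity on GLUMA application". The sample size is for detecting a statistical difference, with alpha 0.05 and effect size 0.2. The tests are Kruskal-Wallis across six arms and, in the SAP overview, a Mann-Whitney test of the two controls only: "whitney U test was used to assess the post operative sensitivity among the control groups". The Brief Summary is less restrictive and mentions Mann-Whitney among the different groups.

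The Procedure section observes that the self-etch Gluma-prior "group consistently showed the lowest VAS scores". It continues "Given the minimal differences in outcome scores among the other groups", concludes that "most treatment protocols were non-inferior" to that arm, and on that basis interprets the trial as "evaluating whether the other etching and desensitizing protocols were not clinically worse than the most effective group".

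The only interval is at 1 week, for total-etch Gluma-after against self-etch Gluma-prior: estimate +0.18, one-sided 95% lower limit +0.003, dispersion 0.1077. The text reads it as reduced sensitivity in the self-etch arm.

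**The concern.** Non-inferiority means ruling out a deficit as large as a stated margin against a stated comparator. Here the margin is missing and the comparator was identified from the outcome data. Small observed differences and non-significant difference tests cannot fill that gap.

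Two things are at stake. Two of the five arms covered by the conclusion are the no-desensitizer controls, so the sentence can be read as saying that omitting Gluma is about as good as the best Gluma arm. And the question the trial set out to answer has no direct comparison: no reported test or interval sets a Gluma arm against the control of its own adhesive system.

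**Working it through.** **1. Does the sample size contain a margin?** For a six-group one-way ANOVA F-test with Cohen's f = 0.2 and alpha 0.05, total N is 330 at 80% power, 420 at 90% and 504 at 95%. The plan's 504 is reproduced at 95% power. Neither the power nor the effect-size metric is stated, so both are assumptions. On this reading 0.2 is an effect to detect, not a margin.

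**2. The reported interval.** The 1-week means (SD) are 0.26 (0.95) and 0.08 (0.27).
- SE with 84 per arm = √(0.95²/84 + 0.27²/84) = 0.1078 (printed 0.1077).
- Lower limit = 0.18 − 1.645 × 0.1077 = +0.003, as printed.
- Higher scores are worse, so the limit that matters for non-inferiority is the upper one: 0.18 + 1.645 × 0.1077 = 0.357.

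The pair is the highest against the lowest of the six 1-week means.

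**3. Upper limits for all five arms.** Each arm is compared with self-etch Gluma-prior: d + 1.645 × √(s₁²/n₁ + s₂²/n₂). Means and SDs come from the SAP table of means. Ns come from the Kruskal-Wallis ranks table (86, 94, 86, 82, 80, 76; the blank self-etch control N at 48 h is taken as 82).

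| Arm | 24 h | 48 h | 1 week |
|---|---|---|---|
| Total-etch control | 0.375 | 0.529 | 0.275 |
| Total-etch Gluma-prior | 0.531 | 0.562 | 0.296 |
| Total-etch Gluma-after | 0.265 | 0.418 | 0.356 |
| Self-etch control | 0.714 | 0.564 | 0.118 |
| Self-etch Gluma-after | 0.671 | 0.525 | 0.242 |

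Arms passing out of five, under margins assumed only for illustration:

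| Margin | 24 h | 48 h | 1 week |
|---|---|---|---|
| 0.1 | 0 | 0 | 0 |
| 0.2 | 0 | 0 | 1 |
| 0.3 | 1 | 0 | 4 |
| 0.5 | 2 | 1 | 5 |
| 1.0 | 5 | 5 | 5 |

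**4. Which N?** The N-weighted mean ranks average 126.50 at all four times. That is (252 + 1)/2; 504 observations would give 252.5. The control-versus-control ranks average 42.50, which fits 84 observations; 168 would give 84.5. A group of 86 cannot have a mean rank below (86 + 1)/2 = 43.5, yet 36.83 and 40.67 are printed.

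The interval's SE fits a third figure, 84 per arm; the printed 86 and 80 would give 0.1068. The table of means does not fit 84: if scores are whole numbers, 7 of its 24 means cannot arise with n = 84. For example, 1.72 falls between 144/84 = 1.714 and 145/84 = 1.726. All 24 can arise at the printed Ns and at half of them.

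**5. Effect of halving the Ns.** The upper limits become 0.342 to 0.820 (24 h), 0.487 to 0.642 (48 h) and 0.150 to 0.428 (1 week). The +0.003 lower limit becomes 0.18 − 1.645 × 0.151 = −0.068.

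**The case against.** The SAP does not rest the label on results alone: Type of Analysis offers a definition and a marginal-benefit rationale. The conclusion is hedged as what the data suggest, and the Brief Summary never mentions non-inferiority, so it is not the trial's headline. Taking the lowest-mean arm as reference tends to make the others look worse, so the choice does not flatter the claim. A pre-specified margin might also exist outside these documents. All of this stands, and the fix allows for the last point. None of it supplies a margin or a test.

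Four stronger readings are tempting but unsupported.

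- **That the other arms are shown to be inferior.** The +0.003 lower limit concerns a pair picked from the extremes and turns negative at half the Ns. With a margin of 1.0, every arm would pass.
- **That the comparator is unstable.** By mean rank self-etch Gluma-prior is only third lowest at 24 h (125.30, against 117.62 and 122.94), but it is lowest at 48 h and 1 week.
- **That Gluma works in that arm.** Against its own control the mean differences are −0.46 at 24 h and −0.38 at 48 h. Holm-adjusted p-values across the 12 Gluma-versus-own-control contrasts are 0.032 and 0.008 at the printed Ns, but 0.39 and 0.20 at half. These are z-tests on means; Mann-Whitney p-values for these contrasts cannot be derived from the tables. The pre-operative gap, 0.63 − 1.88 = −1.25, was larger than either.
- **That Gluma adds nothing.** At 1 week the four Gluma-minus-control differences run from −0.04 to +0.09. With N and scale unresolved, that is not evidence of equivalence.

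**Conclusion.** The non-inferiority conclusion has no margin, no comparator fixed in advance and no test behind it. It is unsupported rather than refuted, and it should not stand in the SAP. Between none and all five arms could be called non-inferior, depending on the margin chosen, and this holds at the printed Ns and at half of them. The primary question has no direct comparison.

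The missing margin and the data-derived comparator are read straight from the text and need no assumption. The limits are normal approximations to skewed scores, taken from rounded means and SDs. They also depend on an N and a scale that the documents leave inconsistent, so they show how far the answer depends on the margin and are not results to report.

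**What to change.** 1. Delete the classification in Type of Analysis and the non-inferiority interpretation and conclusion in Procedure, unless the sponsor can produce a margin and comparator documented before the data were seen. Set no margin now.
2. Stop presenting the highest-versus-lowest 1-week pair as the treatment effect.
3. Before any new analysis, reconcile the analysed N: printed totals of 504 and 168, mean ranks that fit 252 and 84, and an interval SE that fits 84 per arm although the table of means does not. State whether the 1-week score is VAS, as the tables label it, or Schiff, as the Outcome Measures section describes. Explain how a scale running from 1 to 10 gives post-operative means of 0.03 to 0.66.
4. Then report each Gluma arm against the no-desensitizer control of the same adhesive system at 24 h, 48 h and 1 week: four arms × three times = 12 contrasts, labelled as not pre-specified. Use one multiplicity approach for p-values and intervals, for example Holm-adjusted Mann-Whitney p-values with location-shift intervals at a matching simultaneous level. Holm p-values beside unadjusted intervals could contradict each other: at half the Ns the unadjusted 24 h interval for self-etch Gluma-prior (−0.89 to −0.03) excludes zero while the Holm p is 0.39.
5. Add a sensitivity analysis adjusted for pre-operative VAS, because the arms differed at baseline (p = 0.003). Describe contrasts that do not reach significance as inconclusive, not as non-inferior.

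The cost is one data reconciliation, a modest re-analysis of data already held, and rewording of two SAP sections and the reported estimate. The sponsor loses the non-inferiority claim, and the new contrasts are post hoc and may prove inconclusive.

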Intervention description for **Arm 4: Self Etch Control group (No desensitizer application)** where no desensitizer was applied after preparing the cavity two coats of Universal adhesive (3M ESPE Single Bond Universal Adhesive, Germany) were applied by scrubbing with a micro brush, for 20 s per coat. When the surface became shiny, it was light-cured for 20s (Woodpecker LED, Guilin, China). After curing the adhesives, placement of Composite (Charisma Smart, Kulzer GmbH, Germany in increments (1–2 mm thick) by layering technique to reduce polymerization shrinkage.

Intervention description for **Arm 5: Self Etch Gluma desensitizer application prior to etching** in this group a small amount of Gluma Desensitizer (Kulzer GmbH, Germany) was applied to the prepared dentin surface for 30-60 seconds, and then gently dried with air until the surface is no longer shiny. Finally, rinse thoroughly with water and suction. Followed by two coats of Universal adhesive (3M ESPE Single Bond Universal Adhesive, Germany) were applied by scrubbing with a micro brush, for 20 s per coat. When the surface became shiny, it was light-cured for 20s (Woodpecker LED, Guilin, China). After curing the adhesives, placement of Composite (Charisma Smart, Kulzer GmbH, Germany in increments (1–2 mm thick) by layering technique to reduce polymerization shrinkage.

Intervention description for **Arm 6: Self Etch Gluma desensitizer application after self-etch adhesive usage** two coats of Universal adhesive (3M ESPE Single Bond Universal Adhesive, Germany) were applied by scrubbing with a micro brush, for 20 s per coat. When the surface became shiny, it was light-cured for 20s (Woodpecker LED, Guilin, China). After curing the adhesives a small amount of Gluma Desensitizer (Kulzer GmbH, Germany) was applied to the prepared dentin surface for 30-60 seconds,

and then gently dried with air until the surface is no longer shiny. Finally, rinse thoroughly with water and suction. Placement of Composite (Charisma Smart, Kulzer GmbH, Germany in increments (1–2 mm thick) by layering technique to reduce polymerization shrinkage.

Outcome measures

The primary outcome of this clinical trial is to evaluate the effectiveness of GLUMA in controlling the immediate post treatment sensitivity following occlusal composite restorations. Hence, all the patients were assessed for post restoration sensitivity after 24 hours, 48 hours and at the end of one week.

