A significance level of $p < 0.05$ was considered statistically significant throughout the analysis. In the present study, the Kruskal-Wallis test was used to compare six desensitizer groups at different time intervals (Pre-operative, 24 hours, 48 hours, and 1 week post-operatively) based on Visual Analog Scale (VAS) scores. Since each time point represents a distinct clinical endpoint, a separate Kruskal-Wallis test was conducted for each, yielding **individual p-values** corresponding to each time point. As the Kruskal-Wallis test does not permit aggregation of multiple outcomes into a single p-value, **a common p-value is not statistically appropriate**.

Ranks

	Desensitizer Group	N	Mean Rank	P Value ^a
Pre Op VAS	Total etch control	86	105.48	0.003
	Total etch Gluma prior to etching	94	141.70	
	Total etch Gluma after etching	86	116.12	
	Self etch control	82	142.30	
	Self etch Gluma prior to etching	80	106.20	
	Self etch Gluma after etching	76	147.55	
	Total	504		
Post Op sensitivity 24hr VAS	Total etch control	86	125.47	0.126
	Total etch Gluma prior to etching	94	122.94	
	Total etch Gluma after etching	86	117.62	
	Self etch control	82	136.49	

	Self etch Gluma prior to etching	80	125.30	
	Self etch Gluma after etching	76	132.62	
	Total	504		
Post Op sensitivity 48hr VAS	Total etch control	86	131.74	0.050
	Total etch Gluma prior to etching	94	127.98	
	Total etch Gluma after etching	86	123.48	
	Self etch control		132.76	
	Self etch Gluma prior to etching	80	114.36	
	Self etch Gluma after etching	76	128.18	
	Total	504		
Post Op sensitivity 1 week VAS	Total etch control	86	124.24	0.013
	Total etch Gluma prior to etching	94	130.96	
	Total etch Gluma after etching	86	124.38	
	Self etch control	82	129.76	
	Self etch Gluma prior to etching	80	115.00	
	Self etch Gluma after etching	76	134.53	
	Total	504		

p < 0.05 denotes statistically significant difference. All the values exhibit non – statistically significant difference. Statistical test applied *

Kruskal – Wallis test

Ranks

	Desensitizer Group	N	Mean Rank	*P Value
Pre Op VAS	Total etch control	86	36.83	0.012
	Self etch control	82	48.45	

	Total	168		
Post Op sensitivity 24hr VAS	Total etch control	86	40.67	0.337
	Self etch control	82	44.41	
	Total	168		

p< 0.05 denotes statistically significant difference. All the values exhibit non – statistically significant difference except the pre operative pain scores. Statistical test applied * Mann Whitney U test

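### Post-operative sensitivity is tested separately at 24 hours, 48 hours and 1 week, each at 0.05, with no primary time point and no multiplicity adjustment

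*Combined protocol and SAP*

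**What the plan says.** Outcome measures (Detailed Description) defines a single primary outcome: "The primary outcome of this clinical trial is to evaluate the effectiveness of GLUMA in controlling the immediate post treatment sensitivity following occlusal composite restorations". It continues that "all the patients were assessed for post restoration sensitivity after 24 hours, 48 hours and at the end of one week". Neither that section nor the SAP ranks the three times or names one as primary.

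In the SAP, under Procedure, a six-group Kruskal-Wallis test "was used independently for each time point", and p < 0.05 "was considered statistically significant throughout the analysis". The reason offered is: "Since each time point represents a distinct clinical endpoint, a separate Kruskal-Wallis test was conducted for each, yielding" a p-value for each, and therefore "a common p-value is not statistically appropriate". The pre-operative score is listed alongside the three post-operative scores in this scheme. No adjustment, hierarchy or gatekeeping procedure appears.

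The printed p-values are 0.003 (pre-operative), 0.126 (24 hours), 0.050 (48 hours, called borderline) and 0.013 (1 week, called significant).

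The sample size section uses one alpha: "a sample size of 504 restorations was calculated to be sufficient for detecting statistical difference using G* power software (α probability error – 0.05", with "effect size – 0.2".

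**The concern.** Three tests of one primary outcome, each at 0.05, give three chances of a nominally significant result when Gluma and the adhesive systems make no difference. The sample size was set for one test at 0.05, so the plan's nominal error rate and the error rate across its primary tests differ.

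The SAP's argument answers another question. That Kruskal-Wallis does not pool several outcomes into one p-value is a reason to report three p-values. It is not a reason to leave them unadjusted. Holm and Bonferroni work on separate p-values and need no pooled test. Calling the time points distinct endpoints makes the case for adjustment stronger.

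At stake is how a mixed result is read. The SAP prints one non-significant, one borderline and one significant post-operative result, and has no rule for what that combination says about the primary outcome.

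**Working it through.** **1. The plan's own figure.** Inputs: total 504, alpha 0.05, effect size 0.2 (Sample Size Calculation) and six arms. Power and the type of effect size are not stated. Assume Cohen's f = 0.2 in a one-way ANOVA, with noncentrality λ = N·f² = 504 × 0.04 = 20.16 on 5 and 498 degrees of freedom. Power is then 95.2%, and 504 is the smallest balanced total that reaches 95%. So 504 is reproduced for one test at 0.05, under an assumed 95% power.

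**2. Error rate for three tests at 0.05.**
- Independent tests: 1 − 0.95³ = 1 − 0.857375 = 14.3%.
- Upper bound under any dependence: 3 × 0.05 = 15%.
- Perfectly dependent tests would give 5%.

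**3. Correlated tests.** The correlation between time points is not in the documents, so it is varied here. Three six-group Kruskal-Wallis tests were simulated under the null with the printed arm sizes (86, 94, 86, 82, 80, 76), 10,000 trials per setting. Simulation error is about ±0.7 percentage points. The coarse version puts 80 to 90% of scores in the lowest category, which is an assumption suggested by the low printed means (0.03 to 0.66 post-operatively). Its correlation is that of the underlying continuous scale.

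| Correlation | Continuous scores | Coarse scores |
|---|---|---|
| 0 | 14.2% | 13.5% |
| 0.3 | 13.9% | 14.0% |
| 0.5 | 12.9% | 13.1% |
| 0.7 | 11.3% | 13.2% |
| 0.8 | 9.9% | 12.3% |
| 0.9 | 8.7% | 11.4% |
| 0.95 | 7.3% | 10.3% |

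Every setting exceeds 5%.

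**4. Holm on the printed post-operative p-values.** Order them and multiply by 3, 2 and 1:
- 1 week: 0.013 × 3 = 0.039
- 48 hours: 0.050 × 2 = 0.100
- 24 hours: 0.126 × 1 = 0.126

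**5. Are the printed p-values sound?** With N observations the average rank must be (N + 1)/2: 252.5 for 504 and 126.5 for 252. At 1 week, weighting the mean ranks by the printed arm sizes:

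(86 × 124.24 + 94 × 130.96 + 86 × 124.38 + 82 × 129.76 + 80 × 115.00 + 76 × 134.53)/504 = 63,756.16/504 = 126.50.

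The other three time points also give 126.50 (the blank arm size at 48 hours is taken as 82, as at the other times). The two-control comparison shows the same pattern pre-operatively: (86 × 36.83 + 82 × 48.45)/168 = 42.50 = (84 + 1)/2, although the table states 168. The ranks therefore fit half the stated number of observations. Which number produced the p-values cannot be settled from the documents.

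**The case against.** The strongest reply is that adjustment reverses no classification. The 1-week result stays below 0.05, 24 hours stays above it, and 48 hours, printed as 0.050, was not below 0.05 to begin with. That stands, and it limits the weight of the point. What changes is that the 48-hour result can no longer be presented as nearly significant.

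A second reply concerns the size. Two arms have identical means and SDs at 24 and 48 hours (0.37±1.05 and 0.28±0.93), which hints at strong dependence, and strong dependence brings the error rate down. This also stands: any narrow range would rest on a correlation that nobody has reported. It does not bring the rate to 5% in any setting examined.

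A reader might go further in four ways that the documents do not support.
- *That the SAP declares success if any one time point is significant.* No section says so. The SAP reports the times separately and draws its conclusion from descriptive means and a non-inferiority reading. The familywise rate applies only if one significant time point is taken as an effect on the primary outcome.
- *That four tests should be counted, giving 1 − 0.95⁴ = 18.5%.* The fourth is the pre-operative comparison, which is not part of the primary outcome and cannot show a treatment effect.
- *That the 1-week result is shown to be a chance finding.* On the printed p-values it survives Holm.
- *That on 252 observations nothing would be near significance.* Recomputing from the printed mean ranks with halved arm sizes, the pre-operative test gives p = 0.012 before tie correction, and the correction can only lower it. At 1 week the result depends on the unreported share of ties: about 0.88 with none, 0.46 if 85% share the lowest score, 0.25 at 90% and 0.03 at 95%.

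It is also fair to say that Holm, chosen now, is itself chosen after the results are known, and that it does not cover the one-sided 1-week contrast between two arms reported at the end of the SAP. Both are limits of the remedy. Neither is a reason to leave the three tests unadjusted.

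**Conclusion.** The concern holds. The primary outcome is tested three times at 0.05 without a primary time point or adjustment, and the reason given does not justify it. If one significant time point is read as an effect on the primary outcome, the false-positive rate is about 14% for independent tests. It is roughly 7 to 14% over correlations from 0 to 0.95, and about 10 to 14% if scores are coarse and mostly at the lowest value. The intended rate is 5%. The direction is firm. The size rests on an assumed correlation and score distribution.

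The practical consequence is moderate. On the printed values the 1-week result remains significant at 0.039 and the 48-hour result moves to 0.100. Both adjusted figures depend on p-values that sit beside mean ranks fitting 252 observations, so they are provisional until checked.

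**What to change.** First check the Kruskal-Wallis p-values against the data and state how many observations each test used. Then apply Holm's adjustment to the three post-operative tests and report the adjusted p-values beside the unadjusted ones. State in the SAP that the adjustment is post hoc. Using all three times avoids naming a primary time point now, which would be a choice made with the results in view. Show the pre-operative comparison as baseline description only, outside the family of tests.

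The cost is a short SAP addition, three adjusted p-values and slightly less favourable results. No new data are needed. As a guide to the power given up, under the ANOVA reading above, testing at the Bonferroni level 0.05/3 = 0.0167 with 504 restorations lowers power at a single time point from 95.2% to 89.1%. Holm never does worse than that.

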DESINSENSITIZING AGENT	Pre Op VAS	Post Op VAS (24 hrs)	Post Op VAS (48 hrs)	Post Op VAS (1 week)
	Mean±SD	Mean±SD	Mean±SD	Mean±SD
Total etch control	0.86±1.67	0.37±1.05	0.37±1.05	0.21±0.77
Total etch Gluma prior to etching	1.72±2.15	0.49±1.33	0.40±1.12	0.23±0.81
Total etch Gluma after etching	1.16±2.07	0.28±0.93	0.28±0.93	0.26±0.95
Self etch control	1.88±2.25	0.66±1.32	0.41±1.00	0.12±0.33
Self etch Gluma prior to etching	0.63±1.05	0.20±0.46	0.03±0.16	0.08±0.27
Self etch Gluma after etching	2.11±2.40	0.61±1.31	0.37±0.97	0.21±0.53

- **ESTIMATION PARAMETER:** Mean Difference (Final Values)

ESTIMATED VALUE:

The mean post-operative sensitivity at 1 week was 0.18 units lower in the **Self-etch Gluma prior to etching** group compared to the **Total etch Gluma after etching** group, indicating that the former resulted in reduced sensitivity following restoration.

CONFIDENCE INTERVAL: 95%

NUMBER OF SIDES: 1 – sided

LOWER LIMIT:

Estimation Parameter: Mean Difference (Final Values)

Estimated Value: +0.18

Lower Limit (95% CI, one-sided): +0.003

Parameter Dispersion Type: Standard Deviation

Dispersion Value: 0.1077

The dispersion represents the standard deviation of the difference in mean post-operative sensitivity between the two groups.

Age limits: Patient aged between 15 to 70 years of both the gender were included

Healthy volunteers only/ with disease and why: The reason only healthy individuals are often enrolled because this helps to ensure that any observed effects are specifically related to dentin hypersensitivity and not influenced by other factors, such as an impaired immune response that could be present in individuals with certain systemic conditions.¹²

Investigator's Info:

First name: [name] **Middle name:** Nil **Last name:** [name]

Degree: MDS (Master of Dental Surgery)

[contact]

Email ID: [contact]

College Info: CSI College of Dental Sciences and Research, Madurai (CSICDSR)

(Affiliated under TN [name] University, Chennai, India)

Individual Patient sharing: Individual patient details are often not shared in this research due to concerns about privacy, confidentiality, and potential harm to participants, as well as practical and logistical challenges.¹³

References:

1. Porto I. Postoperative sensitivity on direct resin composite restorations: Clinical practice guidelines. *Indian J. Restor. Dent.* 2012; 1:1–12.

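### At one week the rank table and the mean table hold different data for the self-etch Gluma-prior arm, so p = 0.013 and the 0.18 estimate do not describe the same data

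*Combined protocol and SAP*

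**What the plan says.** All the figures are in the Statistical Analysis Plan.

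- The Procedure section reports "1-week VAS: $p = 0.013$ (significant"). This is the only post-operative Kruskal-Wallis test it labels significant; 24 hours is labelled not significant and 48 hours borderline.
- In the one-week block of the first Ranks table, the row for the arm at issue is "Self etch Gluma prior to etching 80 115.00" (printed N, then mean rank), and the row for the control arm with the same adhesive is "Self etch control 82 129.76". The other four one-week mean ranks are 134.53 for self-etch Gluma-after (N 76), 130.96 for total-etch Gluma-prior (N 94), 124.38 for total-etch Gluma-after (N 86) and 124.24 for the total-etch control (N 86). The printed Ns add to 504. The footnote to this table describes every value as non-significant.
- The table of mean VAS gives the self-etch Gluma-prior arm 0.08±0.27 at one week and the total-etch Gluma-after arm 0.26±0.95.
- The Estimated Value entry states: "The mean post-operative sensitivity at 1 week was 0.18 units lower in the" first of these arms than in the second, and concludes that sensitivity was reduced. The one-sided 95% lower limit is +0.003 and the dispersion value is 0.1077.

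**The concern.** A mean rank and a mean with SD for the same arm at the same visit should come from the same scores. When most scores are 0, both can be traced back to a handful of non-zero values, so the two tables can be compared exactly. For the self-etch Gluma-prior arm at one week they disagree.

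This arm matters. The Procedure section names it as lowest at every time point and uses it as the reference for the non-inferiority reading. The only post-operative p-value called significant rests on its ranks, and the only effect estimate rests on its mean. If the two have different data behind them, the test does not support the estimate and the estimate does not describe the test.

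**Working it through.** **1. How many records are behind the ranks.** The N-weighted average of the mean ranks must equal (N+1)/2. Using half of each printed N (43, 47, 43, 41, 40, 38; total 252):

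(43×124.24 + 47×130.96 + 43×124.38 + 41×129.76 + 40×115.00 + 38×134.53)/252 = 31,878.08/252 = 126.50 = (252+1)/2.

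On 504 records the average would be 252.5. The printed ranks therefore come from 252 records.

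**2. What the printed means and SDs imply.** Whole-number scores are assumed, with 0 for no sensitivity.

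- Self-etch control, 0.12±0.33, n = 41: the scores add to 5. Five scores of 1 give SD √[(5 − 25/41)/40] = 0.33. A set with a 2 (2,1,1,1) gives 0.40. So it is five 1s.
- Self-etch Gluma-prior, 0.08±0.27, n = 40: the scores add to 3 (3/40 = 0.075). Three scores of 1 give SD √[(3 − 9/40)/39] = 0.27. A set (2,1) gives 0.35. So it is three 1s.

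**3. A bound using only these two arms.** If both are as printed, their mean ranks differ by (5/41 − 3/40) × (rank of a 1 − rank of a 0). Two ranks among 252 differ by at most 251, so the gap is at most 0.04695 × 251 = 11.8. The printed gap is 129.76 − 115.00 = 14.76.

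**4. Joint fit of all six arms.** All whole-number score sets matching the one-week means and SDs at these Ns were listed.

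- With the self-etch Gluma-prior arm at three 1s there are 8 joint sets. Its mean rank runs from 120.69 to 123.50. In the closest set the largest miss is 120.69 − 115.00 = 5.69.
- With that arm all zero and the other five as printed, one set fits. It has 229 zeros (shared rank 115), 13 ones (236), 3 twos (244), 4 threes (247.5), 2 fours (250.5) and 1 five (252).

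| Arm | n | Non-zero scores | Mean rank | Printed |
|---|---|---|---|---|
| Total-etch control | 43 | 3,3,3 | 115 + 397.5/43 = 124.24 | 124.24 |
| Total-etch Gluma-prior | 47 | 5,2,1,1,1,1 | 115 + 750/47 = 130.96 | 130.96 |
| Total-etch Gluma-after | 43 | 4,4,3 | 115 + 403.5/43 = 124.38 | 124.38 |
| Self-etch control | 41 | 1,1,1,1,1 | 115 + 605/41 = 129.76 | 129.76 |
| Self-etch Gluma-prior | 40 | none | 115.00 | 115.00 |
| Self-etch Gluma-after | 38 | 2,2,1,1,1,1 | 115 + 742/38 = 134.53 | 134.53 |

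**5. Does the method create the mismatch?** Applied to 48 hours, it finds one score set matching all six means, SDs and mean ranks, with this arm's 0.03±0.16 as a single score of 1. Its p with each record doubled is 0.0499, against the printed 0.050. The conflict is confined to one arm at one visit.

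**6. The p-value** (Kruskal-Wallis, tie-corrected; other five arms as in the table).

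| Self-etch Gluma-prior arm | Mean rank | p, 252 records | p, each counted twice |
|---|---|---|---|
| All zero | 115.00 | 0.21 (H = 7.18) | 0.0133 (H = 14.39) |
| Three scores of 1 | 122.58 | 0.75 | 0.38 |

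The printed 0.013 is reproduced only in the all-zero, doubled cell. Over all 8 sets that fit the mean table, p is 0.75 to 0.88 on 252 records and 0.38 to 0.61 doubled.

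**7. The estimate and its limit.**

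- Printed figures: 0.26 − 0.08 = 0.18. SE = √(0.95²/84 + 0.27²/84) = 0.10776, and 0.18 − 1.645 × 0.10776 = 0.0027. These match 0.1077 (truncated) and +0.003.
- With 43 and 40: SE = √(0.95²/43 + 0.27²/40) = 0.151, limit 0.18 − 1.645 × 0.151 = −0.07.
- Arm all zero: difference 11/43 − 0 = 0.26. With 43 in the comparison arm, SE = 0.95/√43 = 0.145 and the limit is 0.26 − 1.645 × 0.145 = +0.02.

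**The case against.** The strongest reply is that little turns on this. The discrepancy is three scores of 1 in 40 patients, the arm has the lowest one-week mean either way (0.00 or 0.08), and the difference is 0.18 or 0.26 on a scale that runs to 10. One-week VAS is also not clearly the endpoint, because Outcome Measures assigns the one-week assessment to the Schiff scale. The footnote to the rank table already denies significance. All of this is fair, and it limits the clinical weight of the point. It does not remove the fact that the only significant post-operative test and the only estimate use incompatible data.

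Three stronger readings are tempting, and the documents do not support them.

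- A reader might infer that this mismatch settles significance, so that p = 0.013 stands if the rank table is right. It does not: on the 252 records behind the ranks, the all-zero version gives 0.21. Nor is +0.003 safe if the mean table is right, since it needs 84 per arm.
- A reader might take 115.00 = (229+1)/2 as proof on its own that every score was 0. It is not. With 211 zeros (shared rank 106) and three non-zero scores averaging rank 226, the arm's mean rank is (37×106 + 3×226)/40 = 115.00. The all-zero result needs the joint fit.
- A reader might suppose that the fit holds at the printed Ns as well. Score sets were listed only at half the printed Ns, and no file of 504 records can give ranks averaging 126.50. Counting twice here means exact duplication of 252 records.

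**Conclusion.** The point holds in a limited form: the rank table and the mean table use different one-week data for the self-etch Gluma-prior arm. The p-value of 0.013 needs this arm at 0.00; the estimate of 0.18 needs it at 0.08, and becomes 0.26 if the arm is all zero. Whether the one-week test is significant depends first on the record count. At 252 records neither version is significant (0.21 or 0.75).

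The conclusion assumes whole-number scores and 0 for no sensitivity. The protocol describes a 1–10 scale, but arm means below 1 require zeros. The all-zero reading also takes the other five arms' means and SDs as correct. The bound in step 3 needs only the self-etch control arm. The documents cannot show which version of the arm is right, nor how the difference arose.

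**What to change.** 1. Establish the true number of records at one week: 252 or 504.
2. Check the one-week scores of the self-etch Gluma-prior arm against source.
3. Rerun the rank table, p-value, mean table, mean difference, dispersion and lower limit from one locked file. Replace every figure that changes, which may include both p = 0.013 and the 0.18 with its +0.003.
4. Until that is done, withdraw the significant label at one week and the statement that this arm reduced sensitivity.
5. Reconcile the footnote under the first rank table, which calls all values non-significant, with the Procedure section.

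The cost is a check of about 40 records by the rank arithmetic (80 as printed), a record count and one rerun. The downside is that the only post-operative result called significant may be lost.
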